6.7 BASELINE, TIME WINDOWS AND CALCULATED VISITS

Study days and visits will be labelled according to the flowchart in the CTP.

Unless otherwise specified baseline is defined as the time point closest to but prior to the first administration of study medication. If no time is specified and the date is the same as the first administration date, then it will still be considered baseline if not specified otherwise. If there

is no measurement earlier than the first administration of study medication, then no baseline will be derived.

Laboratory values:

Baseline is defined as the latest time point before the very first administration of study medication. For laboratories where not only the examination date but also time are recorded, examination time has to be taken into account when defining baseline. That is, a laboratory value on the same date as the first administration of study medication is considered as baseline value only if the time of laboratory assessment is before or the same as the time of first study drug administration.

If any of these times is missing and the date of laboratory assessment is equal to the date of first administration of study medication, then the laboratory assessment will be considered as according to protocol, i.e. as prior to first study medication.

Imaging time windows:

In order to identify whether consecutive imaging time points are missing for a given patient, a nominal time point (6, 12, ... weeks etc.) will be assigned to each and every image. This is achieved by creating windows for every radiological response assessment. These windows are defined in Table 6.7: 1.

Table 6.7: 1 Nominal time points and windows for imaging

| Nominal time point (weeks from start of study medication) | Planned date of scans (relative day*) | Window (days) |
|--|--|----------------------|
| 6 | 43 | 1 to \leq 64 |
| 12 | 85 | 65 to \leq 106 |
| 18 | 127 | 107 to \leq 148 |
| 24 | 169 | 149 to \leq 200 |
| 33 | 232 | 201 to \leq 263 |
| 42 | 295 | 264 to \leq 326 |
| 51 | 358 | 327 to \leq 389 |
| Etc., 9 week interval | Etc. | Etc. |

* the date of the first dose of study medication is Day 1

If a patient does not have an image in one of the windows described above, he/she will be said to have missed an assessment for that time point.

ECG analysis:

Baseline values will be derived from the 1–3 triplicate ECG recordings prior to the first drug administration on Day 1 (refer to [Section 7.8.4](#)).

7. PLANNED ANALYSIS

The labelling and display format of statistical parameters will follow the BI guideline ([8](#)).

All analyses are presented only for Part A, as Part B was cancelled.

For End-of-Text tables, the set of summary statistics is: N / Mean / standard deviation (StD) / Min / Median / Max.

For tables that are provided for endpoints with some extreme data median, quartiles and percentiles should be preferred to Mean, StD, Min and Max.

For time-to-event analysis tables the set of statistics is: number of patients [N(%)], number of patients with event [N(%)], <time to event> [months] followed by P25 (25th percentile), median, P75 (75th percentile) and number of patients censored [N(%)]. If not specified otherwise the duration as well as the time to event will be displayed in months.

Tabulations of frequencies for categorical data will include all possible categories and will display the number of observations in a category as well as the percentage (%) relative to the respective treatment group (unless otherwise specified all patients in the respective patient set whether they have non-missing values or not). Percentages will be rounded to one decimal place. The category missing will be displayed only if there are actually missing values. The denominator of the main categories is defined by the number of patients in the used patient set. The main categories define the denominators of the subcategories. Subcategories should be intended and “[N(%)]” will be displayed only for the main category. If a table includes only categorical data, “[N(%)]” is to be displayed in the column header.

Sort order for general categorical variables: If categories correspond to the collected categories on the eCRF and the table shells do not explicitly specify the ordering, the “default ordering” defined by the eCRF is to be used in such cases. If categories are derived, the ordering as specified in the table shell document should be used; in general ordinal data (e.g. categorised continuous data) are to be displayed in ascending order.

Abbreviations (e.g. Wors.) should not be displayed without any explanations. They will be either spelled out in the table or explained in footnotes (whatever is more reasonable from the programming point of view).

If applicable, conversion from days to weeks, months and years will be as follows:

- Weeks = Days / 7
- Months = (Days * 12) / 365.25
- Years = Days / 365.25

7.1 DEMOGRAPHIC AND OTHER BASELINE CHARACTERISTICS

Descriptive statistics are planned for demographic characteristics, disease history, prior therapies, medical history, alcohol and tobacco use, baseline eastern cooperative oncology group (ECOG) performance status, and baseline disease assessment.

7.2 CONCOMITANT DISEASES AND MEDICATION

Descriptive statistics are planned for this section of the report. Concomitant diseases will be coded similarly as adverse events based on the most current Medical Dictionary for Regulatory Activities (MedDRA) version. Concomitant therapies (CTs) will be coded according to World Health Organization Drug Dictionary (WHO DD). CTs will be classified according to the Anatomical Therapeutic Chemical (ATC) classification system. The third ATC level will be used to categorise CTs by therapy type. In situations where a medical product may be used for more than one equally important indications, there are often several classification alternatives. As appropriate, patients receiving CTs with more than one possible ATC level 3 categories will be counted more than once. Footnotes will clarify this possible double counting in tables.

7.3 TREATMENT COMPLIANCE

Treatment compliance will be listed in the appendix of the CTR. In general, the amount of and time for which BI 891065 is taken will be interpreted in light of treatment exposure, efficacy, and safety. Refer to [Section 5.4.2](#) and [Section 7.7](#) for further details on exposure analysis.

7.4 PRIMARY ENDPOINT(S)

7.4.1 Primary analysis of the primary endpoint(s)

The primary endpoints of Part A are the MTD of BI 891065 and the number of patients with DLTs in the first treatment cycle. The number of patients with DLTs at each dose level will be presented for the first cycle for the MTD evaluation set and for the whole on-treatment period for the treated set separately.

The MTD will be determined by the SMC using recommendations from a Bayesian logistic regression model (BLRM, see CTP Section 7 for details on the model and on the prior). BLM evaluations for the CTR will be performed once using the number of patients with DLTs during the first cycle from the MTD evaluation set and once using the number of patients with DLTs during the whole on-treatment period from the treated set.

Tables and bar charts displaying the posterior probabilities of the true DLT rates being in either the underdosing interval, the targeted toxicity interval or the over toxicity interval will be produced.

7.5 SECONDARY ENDPOINT(S)

7.5.1 Key secondary endpoint(s)

Not applicable as no key secondary endpoints have been defined in the CTP.

7.5.1.1 Primary analysis of the key secondary endpoint(s)

NA

7.5.2 (Other) Secondary endpoint(s)

Part A:

PK endpoints will be analysed descriptively as well. Plasma (and urine) concentrations of BI 891065 will be plotted against time. The calculation of the PK parameters, as well as the descriptive and comparative analysis of the PK parameters, will be based on the methods outlined in Section 7.3.1.2 of the CTP, as well as in (9).

7.7 EXTENT OF EXPOSURE

For Part A, duration of BI 891065 intake will be summarised descriptively. The number of patients with at least one dose reduction of BI 891065 will be displayed descriptively, and the time to first dose reduction of BI 891065 will be analysed descriptively as well using Kaplan-Meier methods based on the treated set. Patients who discontinue BI 891065 without a dose reduction will be censored at the date of the last BI 891065 intake for this analysis. Furthermore, dose intensity of BI 891065 will be calculated.

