Main in- and exclusion criteria	
Main inclusion criteria:
 
• Patients with a confirmed diagnosis of advanced, unresectable and/or metastatic solid tumours, who have failed standard treatment, or for whom no therapy of proven efficacy exists, or who are not amenable to standard therapies• Eastern Cooperative Oncology Group (ECOG) performance status: 0 to 1• Presence of at least one measurable lesion according to response evaluation criteria in solid tumours (RECIST) 1.1 
Main exclusion criteria:
 
• Presence of active invasive cancers other than the one treated in this trial within 5 years prior to screening• HIV, HBV, or HCV infection• Inadequate organ function or bone marrow reserve as demonstrated by laboratory values• Active, known or suspected autoimmune disease• History (including current) of interstitial lung disease or pneumonitis within 5 years• Serious concomitant disease or medical condition affecting compliance with trial requirements• Patients with brain metastases• Patients receiving systemic treatment with any immunosuppressive medication within 1 week prior to treatment start

Proprietary confidential information © 2021 Boehringer Ingelheim International GmbH or one or more of its affiliated companies

Test product(s)	BI 891065 BI 754091 (Part B only)
dose	Part A: BI 891065: starting dose 100 mg once daily Part B: BI 891065: starting dose 200 mg per day BI 754091: fixed dose of 240 mg every three weeks
mode of administration	BI 891065: p.o. BI 754091: i.v. infusion
Comparator product(s)	Not applicable
dose	Not applicable
mode of administration	Not applicable
Duration of treatment	Administration will continue until progressive disease (PD), unacceptable toxicity, or other withdrawal criteria.
Statistical methods	In Parts A and B, dose escalation is guided by Bayesian Logistic Regression Models (BLRMs) with overdose control that will be fitted to binary toxicity outcomes. The estimate of parameters will be updated as data are accumulated using the BLRMs. At the end of the dose escalation, the toxicity probability at each dose level will be calculated to determine an estimate of the MTD and/or the RD. Descriptive analysis (summary statistics) will be used to describe the safety and efficacy endpoints.

Clinical Trial Protocol

Proprietary confidential information © 2021 Boehringer Ingelheim International GmbH or one or more of its affiliated companies

FLOW CHART

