4.1.6 Dose modifications (pause, delay, dose reduction, and discontinuation)

AEs that are immune related should be managed according to the Guidelines for irAE management (as outlined in Appendix [10.2](#)).

For Grade 4 AE/SAEs that are not immune related, study drug should be withdrawn. However, if it can be excluded with high certainty that the event was related to study medication, study drug should be paused, and resumption of study drug may be allowed after discussion with the Sponsor.

For Grade 3 AE/SAEs that are not immune related, study drug should be paused.

For Grade 2 AEs/SAEs that are not immune related but are deemed intolerable by the patient or the treating physician and not responding to appropriate medical management, the physician should decide if a pause of treatment is warranted considering relevant variables such as perceived relatedness to study drug.

If, after a treatment pause of \leq 12 weeks, the non-immune related SAE/AE resolves to baseline or Grade 1 and the physician thinks it is clinically appropriate to restart study drug, then the physician may choose to restart BI 891065 at one dose lower than the dose administered before the pause (except for patients who are receiving the lowest dose allowed) according to Table [4.1.6: 1](#) and Table [4.1.6: 2](#), and BI 754091 at the same fixed dose of BI 754091. Up to two dose reductions of BI 891065 are allowed per patient. If the AE/SAE prompting interruption has unequivocally been excluded to be drug related, reintroduction of BI 891065 at the same dose as prior to the pause may be considered.

There will be no dose reductions or escalations of BI 754091 in any one patient. However, in the event of an infusion-related reaction \leq Grade 2, the infusion rate of BI 754091 may be decreased by 50% or interrupted until resolution of the event and re-initiated at 50% of the initial rate until completion of the infusion. In patients experiencing infusion-related reactions \leq Grade 2, subsequent infusions may be administered at 50% of the initial rate. If an infusion-related reaction is Grade 3 or higher in severity at any point during the study, treatment with BI 891065 and BI 754091 will be permanently discontinued.

As a general rule for Part B, both drugs (BI 891065 and BI 754091) will be stopped, paused, or re-exposed together. Exemptions have to be justified and aligned with the Sponsor in writing.

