If exemption to the dose reduction and pause (e.g., to restart the treatment at the same dose level) is considered, it should be discussed and agreed with the sponsor in advance in writing.

Table 4.1.6: 1

Dose reduction recommendations for BI 891065 in q.d. dosing (up to two dose reductions are allowed per patient)

BI 891065 dose before the pause	BI 891065 dose at restart
400 mg	200 mg
200 mg	100 mg
100 mg	50 mg (lowest dose allowed)

Table 4.1.6: 2

Dose reduction recommendations for BI 891065 in b.i.d. dosing

BI 891065 dose before the pause	BI 891065 dose at restart
200 mg x 2	100 mg x 2
100 mg x 2	50 mg x 2 (lowest dose allowed)

If an intermediate dose which is not listed in the table is investigated, a dose reduction guideline for that dose will be provided separately

There will be no dose reductions or escalations of BI 754091. Modifications of infusion rate are described in section [5.2.6.1.4](#).

The study treatment should be permanently discontinued if any of the following adverse events occur:

- A pause of treatment or delayed start of treatment of more than 12 weeks due to AEs
- Grade 3 or 4 CRS
- Interstitial lung disease (ILD) of any grade
- (For Part B only) Immune related AEs requiring permanent study drug discontinuation as described in Guidelines for Management of Immune-Related AEs (section [10.2](#)):
 - encephalitis, aseptic meningitis, transverse myelitis, or Guillain-Barre syndrome of any grade
 - acquired thrombotic thrombocytopenic purpura of any grade
 - myocarditis of any grade
 - myasthenia gravis, peripheral neuropathy or autonomic neuropathy of grade ≥ 3
 - myositis grade 2 with objective findings (see below), any myositis grade ≥ 3
 - hepatitis grade ≥ 3 (transaminase >5 times ULN or total bilirubin >3 times ULN), recurrent hepatitis grade ≥ 2
 - nephritis grade ≥ 3 , persisting grade 2 nephritis unresponsive to initial steroid therapy or worsening, and recurrent nephritis grade ≥ 2
 - pneumonitis grade ≥ 3 ,
 - rash, bullous dermatoses, severe cutaneous adverse reaction, Stevens Johnson Syndrome, toxic epidermal necrolysis of grade 4, and recurrent rash grade ≥ 3
 - colitis grade 4, and recurrent colitis of any grade
 - uveitis, iritis, episcleritis of grade ≥ 3

Proprietary confidential information © 2021 Boehringer Ingelheim International GmbH or one or more of its affiliated companies

- autoimmune-hemolytic anemia grade ≥ 2
- haemolytic uremic syndrome grade ≥ 3
- immune thrombocytopenia grade 4

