Title of protocol	An open label, Phase I study of BI 891065 monotherapy and combination therapy of BI 891065 and BI 754091 in Asian patients with advanced solid tumours
Global Amendment due to urgent safety reasons	
Global Amendment	
Section to be changed	Flowchart footnote and sections 6.2.3.5 and 10.3.
Description of change	Descriptions to reduce the required study procedures and data collections were added.
Rationale for change	The assessments of primary and secondary endpoints have been completed, and sufficient data have been collected for further endpoint by an interim DBL on 29 Mar 2021. The CTR will be prepared based on the data locked at this interim DBL. As of April 2021, one patient is still receiving the study treatment as per the protocol, but further data collection is no longer needed for the analysis. Therefore, the data to be collected will be reduced to a necessary minimum. The assessments will be performed as medically indicated to monitor the safety at the discretion of the investigator, and the results will be documented in the source data but will not be collected in the eCRF except for AE/SAE and the information about the treatment continuation and study termination.
Section to be changed	Section 5.4.4
Description of change	A statement was added that the genotyping analysis was cancelled.
Rationale for change	Based on the clinical outcome, the sponsor concluded that the genotyping analysis would not result in gaining additional supportive information.

APPROVAL / SIGNATURE PAGE

Document Number: c27190653

Technical Version Number: 5.0

Document Name: clinical-trial-protocol-version-05

Title: An open label, Phase I study of BI 891065 monotherapy and combination therapy of BI 891065 and BI 754091 in Asian patients with advanced solid tumours

Signatures (obtained electronically)

Meaning of Signature	Signed by	Date Signed
Author-Clinical Trial Leader	 A large black rectangular redaction box covering the signature area.	07 May 2021 03:51 CEST
Author-Trial Clinical Pharmacokineticist	 A large black rectangular redaction box covering the signature area.	07 May 2021 07:01 CEST
Approval-Team Member Medicine	 A large black rectangular redaction box covering the signature area.	07 May 2021 08:31 CEST
Approval-Therapeutic Area	 A large black rectangular redaction box covering the signature area.	07 May 2021 14:27 CEST

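### Kaplan-Meier for time to first dose reduction censors permanent discontinuation, a competing event, so the planned quartiles can be reached too early or without enough patients reducing

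*SAP*

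**What the plan says.** SAP 7.7 (Extent of exposure) gives two summaries of dose reduction. The first is a count: "The number of patients with at least one dose reduction of BI 891065 will be displayed descriptively". The second is a time-to-event analysis: "the time to first dose reduction of BI 891065 will be analysed descriptively as well using Kaplan-Meier methods based on the treated set". The censoring rule follows: "Patients who discontinue BI 891065 without a dose reduction will be censored at the date of the last BI 891065 intake". The rule does not distinguish reasons for stopping, and no competing-risk estimate is planned.

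SAP section 7 fixes the content of time-to-event tables: number of patients, number with the event, the three quartiles in months, and number censored. It lists no probability at a fixed time.

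On how treatment ends, the protocol synopsis says: "Administration will continue until progressive disease (PD), unacceptable toxicity, or other withdrawal criteria". Protocol 4.1.6 describes a dose reduction as something that happens when BI 891065 is restarted after a pause for an adverse event. The same section has a list introduced by "The study treatment should be permanently discontinued if any of the following adverse events occur", and also says: "For Grade 4 AE/SAEs that are not immune related, study drug should be withdrawn". The sentence after that one allows a pause and possible resumption if a relation to study drug can be excluded with high certainty.

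**The concern.** Censoring in a Kaplan-Meier analysis assumes that a censored patient remains at risk of the event, at the same rate as those still under observation. Here the event needs continued treatment, because a reduction occurs at restart. After permanent discontinuation the chance of a later reduction is zero. Kaplan-Meier nevertheless passes the stopped patient's weight on to those still on drug, so each later reduction counts for more than one patient.

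Treatment continues until progression, toxicity or another withdrawal criterion. Apart from anyone still on drug at the data cut, every patient without a reduction will therefore be censored under this rule. What is at stake is how a tolerability summary reads: the table could show a median time to first reduction when only one or two patients ever reduced.

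**Working it through.** **Inputs.** The documents state no reduction rate, discontinuation rate or Kaplan-Meier estimate, so there is no figure to reproduce. From the documents: about 12 patients in Part A (protocol 7.6), the censoring rule (SAP 7.7) and the table statistics (SAP section 7). A quartile is taken as the first time at which the curve reaches 25%, 50% or 75%.

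**One reduction, no hazards assumed.** Take n = 12, with one patient reducing and 11 discontinuing without a reduction. Order the 12 first outcomes in time and let the reduction be the k-th, so that 13 - k patients are at risk just before it.

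- 1-KM at end of follow-up = 1/(13 - k).
- Aalen-Johansen cumulative incidence = [(13 - k)/12] × [1/(13 - k)] = 1/12 = 8.3% for every k.

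| Position of the reduction | 1-KM | Cumulative incidence | Quartiles Kaplan-Meier reports |
|---|---|---|---|
| 1st | 1/12 = 8.3% | 8.3% | none |
| 6th | 1/7 = 14.3% | 8.3% | none |
| 9th | 1/4 = 25% | 8.3% | P25 |
| 11th | 1/2 = 50% | 8.3% | P25, median |
| 12th | 1/1 = 100% | 8.3% | P25, median, P75 |

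**Two reductions out of 12.** The cumulative incidence is 2/12 = 16.7% in every order. 1-KM depends on the order:

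- 1st and 2nd: 1 - (11/12)(10/11) = 16.7%.
- 3rd and 9th: 1 - (9/10)(3/4) = 32.5%.
- 5th and 11th: 1 - (7/8)(1/2) = 56.25%. A median is reported with one patient in six reducing.

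When everyone has had one of the two outcomes, the cumulative incidence ends at the crude proportion. Its P25 then needs at least 3 of 12 patients to reduce, its median 6 and its P75 9. Kaplan-Meier has no such link to the count.

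**How often this could matter (hazards are assumptions).** With constant monthly hazards r for reduction and d for discontinuation, 20,000 trials of 12 patients were simulated per setting and followed until every patient had one of the two outcomes. The true final probability of reduction is r/(r + d).

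| r, d | True | Mean 1-KM | P25 reached: KM / CIF | Median reached: KM / CIF |
|---|---|---|---|---|
| 0.02, 0.23 | 8.0% | 22.5% | 33% / 7% | 17% / 0% |
| 0.05, 0.23 | 17.9% | 43.9% | 67% / 37% | 39% / 1% |
| 0.10, 0.46 | 17.9% | 44.2% | 67% / 37% | 39% / 1% |
| 0.10, 0.23 | 30.3% | 64.1% | 90% / 75% | 66% / 12% |

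CIF is the Aalen-Johansen estimate; its mean equals the true value in each row. These rows show the direction and the spread of the effect. They do not predict this trial.

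**The case against.** The best defence is that the SAP already supplies the corrective. The crude number with a reduction is planned in the same paragraph, and the numbers with event and censored stand in the same table as the quartiles. SAP 7.8.1 also tabulates by CTCAE grade, and lists, adverse events leading to dose reduction or permanent discontinuation. A Kaplan-Meier median beside a low count is a different quantity, not a contradiction. If discontinuation were independent of the tendency to reduce, it could be read as the time to reduction were treatment to continue. All of this limits the harm. It does not repair the quartiles: the SAP gives them no such label, and the documents offer no basis for assuming independence.

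It is also true that the excess vanishes if all reductions come before all discontinuations. The documents do not say which order applies.

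A reader might infer three stronger points that the documents do not support:

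- **That discontinuation is often driven by toxicity.** Protocol 4.1.6 shows that some toxicities bypass a reduction, but no frequency is given. Protocol 3.3.4.1 also lists progression, patient choice, non-compliance and other medical reasons. Non-immune Grade 3 events lead to a pause, not directly to withdrawal. The point here needs no link with toxicity.
- **That the SAP lacks a censoring rule for a patient still on treatment at the data lock.** Protocol 11.4 does report that "one patient is still receiving the study treatment as per the protocol". However, SAP 7.3 sends the reader to Section 5.4.2 as well as 7.7 for exposure details, and Section 5.4.2 is not in the public text. The absence of a rule cannot be asserted.
- **That the recommended dose is affected.** Protocol 2.1.1 gives that decision to the SMC on the EWOC criterion, DLTs from all cycles and all available data. Nothing ties this summary to it.

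**Conclusion.** The point holds as a small one. Permanent discontinuation for any reason precludes a later reduction, so 1-KM is never below the cumulative incidence and is strictly above it once a reduction follows a discontinuation. Where this appears is P25, median and P75, and any curve that is plotted; the crude count is not affected. For 12 patients with one reduction, the gap runs from nothing (8.3% against 8.3%) to 100% against 8.3%, depending only on order.

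Probabilities of reduction at, say, 6 or 12 months would be tempting as a measure of size. They would rest wholly on assumed hazards and match no statistic listed in SAP section 7. The simulated rates above carry the same caveat about hazards.

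The analysis is descriptive, untested, in about 12 patients, and outside the MTD, DLT and PK endpoints. The change is a cheap improvement and no trial conclusion depends on it.

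**What to change.** In SAP 7.7, replace the Kaplan-Meier estimate with the Aalen-Johansen cumulative incidence of first dose reduction. Treat permanent discontinuation without a reduction as the competing event, and censor only patients still on treatment without a reduction at the data cut. If Section 5.4.2 already contains a data-cut rule, cross-refer to it. Take P25, median and P75 from that curve, and keep the crude count beside it.

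If Kaplan-Meier is kept, label it as time to reduction while on treatment, resting on the assumption that stopping is independent of the tendency to reduce, and not as the proportion of patients reducing.

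Cost: a change of estimator and a sentence in the SAP; no new data are needed. The drawback is that the median and P25 will often be not reached, which is the accurate result when few patients reduce.
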